7.4.2. Other Secondary Endpoints

7.4.2.1. Proportion of Patients Who Responded to Retreatment During the Retreatment Period

Proportion of patients who responded (MBL volume of < 80 mL) to retreatment with open-label relugolix 40 mg +E2/NETA during the retreatment period among placebo patients whose MBL volume had returned to \geq 80 mL during the randomized treatment period will be summarized descriptively. The point estimate and its corresponding 95% CIs will be provided.

The change and percent change in MBL volume from retreatment initiation will also be summarized descriptively as a continuous variable every 4 weeks after retreatment initiation during the retreatment period.

7.4.2.2. Change and Percent Change from Week 52/Baseline in Menstrual Blood Loss Volume During the Randomized Treatment Period

The change (for all patients) and percent change (for patients who did not have amenorrhea at baseline) in MBL volume from Week 52/baseline will be summarized descriptively as a continuous variable at each visit during the randomized treatment period including Week 76 and Week 104 visits. Observed MBL volume for each timepoint will be used to calculate change and percent change from Week 52/Baseline. In addition, the change and percent change in MBL volume from Week 52/baseline will also be summarized descriptively as a continuous variable at each visit during the cumulative treatment period.

For change and percent change in MBL volume, mixed-effects model will not be used to derive LS means (and 95% CIs) due to skewed distribution of MBL volumes (majority of patients experiencing amenorrhea with MBL volume set as 0 mL at baseline). Descriptive statistics (medians and simple means) will be provided for each treatment group.

Categorical summary of change in MBL volume will be provided by grouping patients into three categories: who had increase, no change, and decrease in MBL volume from Week 52/Baseline over time by visit for cumulative treatment period. A figure will also be provided to display the percentages for each category by treatment group every 12 weeks from Week 52/Baseline up to Week 104.

Besides, the observed MBL values will be categorized into three categories: 0 mL, > 0 to < 80 mL, and ≥ 80 mL. Shift tables will be provided to summarize Week 52/Baseline versus each post-baseline visit for the randomized treatment period and cumulative treatment period. Figures will also be provided to display the percentages for each category by treatment group at Week 52/Baseline, Week 76, and Week 104.

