Patients will receive their last dose of study drug in the OLE study on the day of the Week 52/Baseline visit (as per the OLE study protocol), and the patient will be provided blinded study drug to begin dosing the following day. The first dose of study drug will be selfadministered the next morning following the Week 52/Baseline visit. After the Week 52/Baseline visit, a phone call will occur on Week 52 Day 1 (+ 2 days) to document the time of self-administration of the first dose of study drugs and record any reported adverse events. On-treatment study visits will occur every 4 weeks for a total of 104 Weeks. With the initiation of randomized treatment, patients will collect all stained/soiled feminine products and at the study visits return their feminine products for alkaline hematin testing. A venous blood sample (for hemoglobin) must be collected each time feminine products are returned and sent to the central laboratory conducting the alkaline hematin assessment. If the patient is having cyclic bleeding, the site must document the start and stop dates of the patient's menses corresponding to the collected feminine products. The paper diary recording vaginal bleeding and feminine product use should be reviewed at each visit to assess compliance with feminine product collection.

When the alkaline hematin analysis indicates MBL \geq 80 mL, the patient will be asked to return with onset of the next menses, no later than cycle day #7 (where cycle day #1 is the first day of menstrual bleeding), to begin retreatment with open-label relugolix with E2/NETA. The timing of this visit may necessitate an unscheduled visit. The final dose of randomized treatment should be self-administered by the patient the day prior to presenting for retreatment. The first dose of retreatment with open-label relugolix with E2/NETA will be administered at the clinic visit. Feminine products do not need to be collected with the episode of menstrual bleeding associated with the initiation of retreatment, but once the episode is complete, all stained/soiled feminine products must be collected and returned at subsequent visits for alkaline hematin analysis until MBL < 80 mL is observed for two consecutive collections.

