6.5.1.2. Menstrual Blood Loss as Assessed by the Alkaline Hematin Method

The volume of menstrual blood loss is measured in milliliters using the alkaline hematin method [Hallberg, 1964]. The method involves pummeling used feminine products in a solution and measuring the resulting hematin absorbance against calibration curves. The method is validated in accordance with current FDA Guidance for Method Validations and is an accepted quantitative clinical endpoint for the assessment of heavy menstrual bleeding. The site staff will provide collection kits with standardized and validated feminine products to patients for the collection and assessment of those products to determine menstrual blood loss.

The feminine products will be dispensed and all stained/soiled products will be collected at each visit starting with the initiation of randomized study drug treatment. Product collection will continue at each visit unless heavy menstrual bleeding (MBL \geq 80 mL) is observed. Collection will resume following the initiation of retreatment with open-label relugolix with E2/NETA and continue until MBL is observed to be < 80 mL on two consecutive collections. If the patient is having cyclic bleeding, the site must document the start and stop dates of the patient's menses. Each time the patient submits her feminine products from a menstrual cycle for analysis, a venous blood sample will be collected and sent to with the products to the the laboratory for the alkaline hematin analysis. Details regarding materials, process, and requirements for the menstrual blood loss collection are provided in the Study Reference Manual.

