Patients were to be asked to collect FPs for alkaline hematin analysis and to return them at each visit until the analysis confirmed the return of heavy menstrual bleeding (defined as menstrual blood loss volume of ≥ 80 mL). The patients were then to be offered re-treatment with open-label relugolix +E2/NETA with the onset of the next menses. They were to continue collection of FPs for alkaline hematin analysis until two consecutive analyses confirmed resolution of heavy menstrual bleeding (menstrual blood loss of < 80 mL). Patients who experienced a return of heavy menstrual bleeding (or terminate early because they have a return of heavy menstrual bleeding) but who decline retreatment with open-label study drug were to complete an Early Termination visit and a 30-day Safety Follow-Up visit.

At the Week 104/Early Termination visit, all other patients were to have an assessment of bone mineral density (BMD) via dual-energy x-ray absorptiometry (DXA). Patients were to complete the bleeding diary daily, including compliance with study drug, vaginal bleeding, and use of FPs.

If a patient enrolls directly into another relugolix clinical study upon completion of the Week 104/Early Termination visit, then the Safety Follow-Up visit and the follow-up procedures performed under this protocol may be waived.

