- For by-visit observed data analyses, calculation of percentages will be calculated on the basis of the number of patients with non-missing data as the denominator, unless otherwise specified;

- For other continuous endpoints, the summary statistics will include mean, SD, median, and range (minimum and maximum);
- For time-to-event endpoints, the summary statistics will include median time to event-free survival, 25th and 75th percentiles and number of patients at risk at specified time points;
- For categorical endpoints, the summary statistics will include counts and percentages;
- Confidence intervals, when presented, will generally be constructed at the 95% level. For binomial variables, exact methods will be employed, unless otherwise specified.

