4.4.1. By-Visit Endpoints

By-visit endpoints will be analyzed using observed data, unless otherwise specified. For observed data analyses, missing data will not be imputed and only the observed records will be included.

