7.4.1.1. Time to Relapse (Menstrual Blood Loss Volume \geq 80 mL)

For the endpoint of time to MBL volume \geq 80 mL (event) during the randomized treatment period, time-to-event will be defined as weeks from first dose of the randomized withdrawal study drug to first occurrence of MBL volume of \geq 80 mL. The corresponding menstruation start date will be considered as the event date. Patients without an event will be censored by following the same censoring rules described in Section 7.3.1.2. Kaplan-Meier methods will be used to describe the time to event (relapse) distributions for each study treatment group from which median time to event will be derived. Hazard ratio (95%CI) of relugolix + E2/NETA to placebo for risk of relapse (MBL volume \geq 80mL) will be provided using a proportional hazard model stratified by the stratification factors (pivotal study baseline MBL volume (< 225 ml vs. \geq 225 mL) and duration of exposure to relugolix (28 weeks vs. 52 weeks). p-value for comparison of relugolix + E2/NETA to placebo based on the stratified log-rank test will be provided.

7.4.1.2. Proportion of Patients Who Maintained a Menstrual Blood Loss Volume of < 80 mL at Week 104

The proportion of patients who maintained a menstrual blood loss volume of < 80 mL by Week 104 (52 weeks of the randomized treatment period) as measured by the alkaline hematin method will be analyzed using the same method as that for primary efficacy endpoint described in Section 7.3. It is noted that sustained responder rate at Week 104 (Day 365) will be defined as the KM estimates from the same KM curves and will be analyzed using the same method as for the primary endpoint (see Section 7.3.1).

No subgroup analysis will be performed for this secondary efficacy endpoint.

The proportion of patients who maintained a menstrual blood loss volume of < 80 mL will also be summarized during the cumulative treatment period (including both randomized treatment period and the retreatment period).

The proportion of patients who had a menstrual blood loss volume of < 80 mL at a visit will also be summarized descriptively by visit during the cumulative treatment period (including both randomized treatment period and the retreatment period).

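### On retreatment, product collection stops once a woman has succeeded, but menstrual blood loss is still tabulated by visit with no stated place for her, so these descriptive tables can show response fading when it has not.

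*SAP*

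**What the plan says.** **When collection stops.** Protocol 6.5.1.2 has collection resume when retreatment starts and "continue until MBL is observed to be < 80 mL on two consecutive collections". SAP 2.1 repeats the rule: "They were to continue collection of FPs for alkaline hematin analysis until two consecutive analyses confirmed resolution of heavy menstrual bleeding". Protocol 6.2 exempts the first bleed: "Feminine products do not need to be collected with the episode of menstrual bleeding associated with the initiation of retreatment".

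**What is tabulated after that.** SAP 7.4.2.1 plans change and percent change in MBL from the start of retreatment, which "will also be summarized descriptively as a continuous variable every 4 weeks after retreatment initiation during the retreatment period". The cumulative period joins the randomized and retreatment periods. Over it:

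- SAP 7.4.1.2 plans the proportion below 80 mL, which "will also be summarized descriptively by visit during the cumulative treatment period (including both randomized treatment period and the retreatment period").
- SAP 7.4.2.2 plans MBL change by visit, categories of change with a figure every 12 weeks to Week 104, and tables of three volume classes (0, above 0 to below 80, and 80 mL or more): "Shift tables will be provided to summarize Week 52/Baseline versus each post-baseline visit for the randomized treatment period and cumulative treatment period".

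**How absent readings are treated.** For by-visit endpoints, SAP 4.4.1 says that "missing data will not be imputed and only the observed records will be included". For by-visit percentages, SAP 4.1 uses "the number of patients with non-missing data as the denominator". SAP 7.1.1, on categorical efficacy data, instead keeps missing observations in the denominator as a separate category. Both denominator rules give way only where something else is specified, and neither refers to the other. Table 9 (SAP 7.3.3) codes the eCRF reason for a successful-retreatment stop as N/A for volume and responder status. That table is headed for the randomized period and sets no table denominator. SAP 7.3.2.4 assigns 0 mL for reported amenorrhea and less than 5 mL for reported spotting, but only for intervals before retreatment.

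**The concern.** Retreatment effect is a stated secondary objective, and Protocol 4.2 presents it as a test of whether improvement can be recaptured. In these tables the reading is absent because treatment worked. After the second collection, the women still supplying readings are those who have not yet had two successes in a row. If some women respond consistently and others do not, the remaining group is increasingly made up of the latter. A reader following the 4-weekly table would see medians rise and the proportion below 80 mL fall, and could take that as loss of effect on continued retreatment. The tabulated N falls, but nothing in the table says that it falls through success. The alternative denominator in SAP 7.1.1 does not cure this: recaptured women then sit in a missing row beside women who failed to collect.

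A smaller gap lies next to it. A woman who is amenorrheic on retreatment has no product to return, and the SAP gives no MBL value for her interval.

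**Working it through.** No figure in the plan can be reproduced here, because the documents give neither a recapture rate nor a within-woman correlation. Both are assumed below.

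**Model.** Woman *i* has probability p_i of a reading below 80 mL at every retreatment collection, and leaves after two such readings in a row:

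p_i = Φ((0.8416 + √ρ · b_i) / √(1 − ρ)), with b_i standard normal.

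The mean of p_i is 0.80, so the true proportion below 80 mL is 80% at every collection. The latent correlation ρ is set to 0, 0.5 and 0.9.

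**Collection 3, the earliest exit.**

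- Still collecting = 1 − E[p²]
- Below 80 mL among those still collecting (SAP 4.1 denominator) = (E[p] − E[p³]) / (1 − E[p²])
- Below 80 mL among all retreated women (SAP 7.1.1 denominator) = E[p] − E[p³]

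| Collection 3 | ρ = 0 | ρ = 0.5 | ρ = 0.9 |
|---|---|---|---|
| Still collecting | 36% | 31% | 25% |
| Stopped for success | 64% | 69% | 75% |
| Table under SAP 4.1 | 80% | 60% | 31% |
| Table under SAP 7.1.1 | 29% | 19% | 8% |
| True | 80% | 80% | 80% |

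For ρ = 0.5, 0.603 × 0.313 = 0.189, which is the 19%.

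**Collection 6**, by stepping the same rule forward: 6%, 13% and 18% are still collecting, of whom 80%, 44% and 18% are below 80 mL.

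**Other true rates**, collection 3, SAP 4.1 denominator: at a true 60% the table reads 60%, 45% and 23%; at a true 95% it reads 95%, 78% and 43%.

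**Continuous summary.** If MBL is log-normal with log SD 1 and 80% of readings are below 80 mL, the median is 34 mL at collections 1 and 2. At collection 3 with ρ = 0.5 it is 64 mL. Over log SD 0.7 to 1.5 the shift runs from 44 to 68 mL down to 23 to 57 mL. With ρ = 0 there is no shift.

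**A different model.** Suppose recaptured women are below 80 mL at 95% of readings and the others at 30%, with 80% of women recaptured. The true proportion is 0.8 × 0.95 + 0.2 × 0.30 = 82%. The SAP 4.1 table reads 50% at collection 3 and 32% at collection 5.

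**Week 104 gap between arms**, deliberately extreme. Per 100 women per arm, the plan's assumed Week 76 rates of 40% and 60% (SAP 2.2) are taken as never relapsed. All relapsers are retreated, every recaptured woman has stopped and stays below 80 mL, and all others are at 80 mL or more.

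| Recapture (placebo / relugolix) | True | SAP 4.1 | SAP 7.1.1 |
|---|---|---|---|
| 80% / 80% | 88 vs 92, gap +4 | 40/52 = 76.9% vs 60/68 = 88.2%, gap +11 | 40% vs 60%, gap +20 |
| 80% / 30% | 88 vs 72, gap −16 | 40/52 = 76.9% vs 60/88 = 68.2%, gap −9 | 40% vs 60%, gap +20 |

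The SAP 4.1 gaps therefore hold only under that denominator.

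**The case against.** The strongest reply is that SAP 7.1.1 sits in the efficacy section and already keeps missing observations in the denominator as a separate category, while Table 9 already distinguishes a success stop (N/A) from a failure to collect (Missing). On that reading the categorical tables lose nobody. This stands in part: the SAP 4.1 percentages above rest on one of two competing rules. It does not rescue the tables. Neither rule shows a recaptured woman as a success, and Table 9 says nothing about how an N/A visit enters a by-visit table.

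It is also fair that these are untested summaries with N shown, that the retreatment responder proportion with its confidence interval addresses recapture more directly, and that hemoglobin, anemia, SF-36, PGA, WPAI-UF and UFS-QoL are already summarized over the cumulative period (SAP 7.4.2.6 to 7.4.2.11). All of this lowers the importance. The size is driven by assumption, and with ρ = 0 the SAP 4.1 proportion and the median do not move.

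Three stronger inferences are tempting and are not supported:

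- *The confirmatory results are biased.* The primary and key secondary analyses use randomized-period data, before retreatment.
- *The retreatment responder proportion is wrong.* It can be formed from the readings obtained before the stop. SAP 7.4.2.1 names no time point for it, but that is a separate question.
- *The tables must show fading, or favor one arm.* Fading under SAP 4.1 needs persistence within women, and the direction of any distortion between arms depends on recapture in each.

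**Conclusion.** The mismatch holds for descriptive MBL tables in the retreatment and cumulative periods, and only there. Women stopped for success leave the continuous summaries from the third collection at the earliest; those whose first two readings are not both below 80 mL leave later. In the categorical tables their handling is undetermined between SAP 4.1 with 4.4.1 and SAP 7.1.1. At an assumed constant 80% per collection and correlation 0.5, the third-collection table would read 60% or 19%, according to the rule. Across correlations of 0 to 0.9 the ranges are 80% to 31% and 29% to 8%. The model gives every collection a usable reading, so it ignores the missing amenorrhea rule on retreatment, and it assumes that response does not change over time. The point is minor but worth correcting, because a misread table would bear on a stated secondary objective.

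**What to change.** - In the retreatment and cumulative by-visit categorical tables and figures, state one denominator: all women in the period. Use the existing eCRF reason for a successful-retreatment stop (SAP 7.3.2.5) as its own row, separate both from below 80 mL and from missing. It should not be merged with below 80 mL: merged, collection 3 would read 93%, 88% and 83% at ρ = 0, 0.5 and 0.9, against a true 80%.
- Keep the continuous MBL summaries, but label them as covering only women still collecting, and print N with the number stopped for success.
- Extend the 0 mL amenorrhea and less-than-5 mL spotting assignments of SAP 7.3.2.4 to retreatment intervals before collection stops.

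The cost is SAP text and table shells. No visit, sample or confirmatory test changes. Each table gains a row, and blood loss volume after the stop remains unknown.

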7.4.2.3. Proportion of Patients Whose Menses Has Resumed

This endpoint is defined only for patients who were amenorrheic (ie, had MBL volume of 0 mL at baseline).

7.4.2.3.1. Determination of Resumption of Menses

Patients who were previously amenorrheic will be deemed to resume the menses during a visit window according to the following rules:

- FPs were collected and MBL volume was ≥ 5 mL;

OR

- FPs were collected and MBL volume was < 5 mL; however, there were more than 5 days and more than 3 consecutive days of bleeding with FP use during the visit window per the diary;

OR

- No FPs were returned because patient failed to collect used products per protocol; however, there were more than 5 days and more than 3 consecutive days of bleeding with FP use during the visit window per the diary;

OR

- No FPs were returned due to other reasons that indicate menstruation occurred; also, there were more than 5 days and more than 3 consecutive days of bleeding with FP use during the visit window per the diary.

These were also described in [Table 12](#).

Table 12 Rules for Determining Resumption of Menses by Visit

Feminine Product Collection	Patient's Paper Diary	Resumption of Menses?	Date of Resumption of Menses
Feminine products were collected with observed MBL volume \geq 5 mL	N/A	Yes	Earliest menstruation date recorded in KCAS ^a data for the corresponding feminine product collection
Feminine products were collected with observed MBL volume < 5 mL	> 5 days and > 3 consecutive days of bleeding with feminine product use reported in paper diary	Yes	Earliest menstruation date recorded in KCAS ^a data for the corresponding feminine product collection
Feminine product collection not performed per protocol or no feminine product collection performed due to other reasons which indicate menstruation occurred.	> 5 days and > 3 consecutive days of bleeding with feminine product use reported in paper diary	Yes	Paper diary date of first episode of > 3 consecutive days of bleeding with feminine product use in timeframe corresponding to missed collection.

^a This date has been reconciled against the Menstruation Status data in EDC and is more reliable if irregular bleeding has been reported.

Abbreviations: MBL = menstrual blood loss; N/A = not applicable.

7.4.2.3.2. Resumption of Menses During the Randomized Treatment Period

Proportion of patients whose menses has resumed during the randomized treatment period among those who were amenorrheic at Week 52/Baseline will be summarized by treatment at Week 76 and at Week 104. The point estimate and its corresponding 95% CIs will be provided based on the Kaplan-Meier method as described below in Section 7.4.2.4.

7.4.2.4. Time to Resumption of Menses

For time to resumption of menses among those who were amenorrheic at Week 52/Baseline, time-to-event will be defined as weeks from first dose of the Randomized Withdrawal study drug to first occurrence of the menses resumption during the randomized treatment period. Patients without an event will be censored at last assessment date prior to the last dose of randomized withdrawal study drug before Week 104.

Kaplan-Meier methods will be used to describe the time to event distributions by Week 76 and by Week 104 for each study treatment arm. Difference (95% CI) in the rate of menses resumption between the two treatment groups will be calculated at Week 76 and Week 104 based on the KM estimates. P-value from the unstratified log-rank test for treatment comparison in the KM rates at Week 76 and Week 104 will be provided. See Section 7.1.3 for more details.

7.4.2.5. Proportion of Patients with Menstrual Blood Volume \geq 80 mL at Any Timepoint During the 52-week Randomized Treatment Period

Proportion of patients with menstrual blood volume \geq 80 mL at any timepoint during the randomized treatment period will be summarized by visit based on the Kaplan-Meier estimates. The treatment differences (95% CI) in the proportions at Week 76 and at Week 104 will be provided using the analysis method described above in Section 7.4.1.1.

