- Transvaginal ultrasound, with or without transabdominal ultrasound, and with or without saline or gel contrast, is performed to determine uterine and myoma volumes and to exclude any other uterine or pelvic pathology. To avoid inter-observer and inter-device variations, a single operator will be assigned to a patient and will perform each of the ultrasound scans using the same device as far as possible. Once the transvaginal ultrasound is done, a transabdominal ultrasound may also be done if the uterus cannot be adequately imaged on transvaginal ultrasound; for example, due to enlarged size. Results must be submitted to a central reader.
- ⁿ Bone densitometry (L1-L4, total hip, femoral neck) will be submitted for central reading.
- This procedure is not required at the Early Termination visit in patients whose last dose of study drug was taken during Week 60 or earlier. However, the procedure may be done if it will aid in the evaluation of an ongoing adverse event.
- Patients with a bone mineral density loss of > 7% at their Week 104/Early Termination visit relative to Parent study Baseline measurement will undergo a follow-up bone densitometry scan at 6 (± 1) months and will be contacted to question them about medications and conditions (estradiol, pregnancy) that might affect bone mineral density through the time of follow-up bone densitometry. The follow-up bone densitometry will be submitted for central reading.
- Patients will be dispensed randomized treatment at the Week 52/Baseline visit, for self-administration beginning the following day, Week 52, Day 1. Randomized treatment will be dispensed at subsequent visits until HMB (MBL ≥ 80 mL) is documented by alkaline hematin testing. When HMB has been documented, the patient will be invited for a visit to begin retreatment with open-label study drug. The timing of that visit should be within 7 days of the onset of the patient's next menses (Cycle day 1-7 where Cycle day 1 is the first day of menstrual bleeding).
- Patients will take the first dose of study drugs for this study once daily starting at Week 52, Day 1 (self-administered with phone follow-up). The last dose of study drug will be taken in the clinic during the Week 104/Early Termination visit.
- s Site to call patient and confirm first dose of study drug was taken that day.
- Patients enter diary information on menstruation status and feminine product use.

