4.3. Definitions, Computation, and Convention

4.3.1. Definition of Date of First Dose and Date of Last Dose of Study Drug During the Randomized Treatment Period

The randomized treatment period is the period when a patient was on one of the randomized study drugs (relugolix + E2/NETA or placebo). The date of first dose of study drug is defined as the date when a patient receives the first dose of study drug for the randomized withdrawal study following randomization. The first dose of study drug for the randomized withdrawal study was to be self-administered the next morning following the Week 52/Baseline visit.

The date of the last dose of randomized study drug is defined as the date a patient receives the last dose of randomized study drug in this randomized withdrawal study, prior to re-treatment or on the Week 104 visit date. If the complete date of last dose of study drug is unknown, the last date the study drug was known to have been taken will be used.

4.3.2. Definition of Date of First Dose and Date of Last Dose of Retreatment Drug

The date of first dose of retreatment drug is defined as the date when a patient receives the first dose of retreatment drug (open-label relugolix + E2/NETA). When the return of heavy menstrual bleeding (defined as menstrual blood loss of ≥ 80 mL) was confirmed for a patient during the randomized treatment period, the patient was to be offered retreatment with open-label relugolix + E2/NETA with the onset of the next menses.

The date of the last dose of retreatment drug is defined as the date a patient receives the last dose of retreatment drug in this randomized withdrawal study, prior to or on the Week 104 visit date. If the complete date of last dose of retreatment drug is unknown, the last date the retreatment drug was known to have been taken will be used.

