Week 96 (44 weeks after randomization)	Week 96	X ₁₁	(X ₁₀ +1) – ≤ X ₁₁
Week 100 (48 weeks after randomization)	Week 100	X ₁₂	(X ₁₁ +1) – ≤ X ₁₂
Week 104 (52 weeks after randomization) /EOT	Week 104/EOT	X _{Last} ^c	(Previous Feminine Product Returned Visit +1) – ≤ X _{Last}

^a If feminine products are collected at more than 1 visit within a given visit window (Table 2), the last feminine product collection date will be used to define the time window. If the patient missed the previous visit, a planned study visit date will be used to calculate the window.

^b In the absence of feminine product collection due to amenorrhea the visit date when amenorrhea was reported will be used.

^c Date of last non-missing feminine product collection within the interval from (previous visit end date + 1) to (last dose date + 7 days) (see Section 7.3.2).

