7.4.1.3.2. Amenorrhea During the Randomized Treatment Period

Patients achieving or maintaining amenorrhea during the randomized treatment period at Week 76/EOT (or at Week 104/EOT) are defined as those who meet the definition of amenorrhea at last two consecutive post-baseline visits prior to date of last dose of study drug during the randomized treatment period through Week 76 (or through Week 104) visit.

A key secondary endpoint is the proportion of patients who achieved or maintained amenorrhea at Week 76/EOT during the randomized treatment period.

Patients missing amenorrhea reporting for all visits in the study will not be considered as amenorrheic by Week 76 or Week 104.

Proportion of patients achieving or maintaining amenorrhea at Week 76/EOT and at Week 104/EOT will be summarized by treatment and treatment comparisons will be performed using a stratified Cochran-Mantel-Haenszel test.

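### The censoring rule for time to resumption of menses can remove event-free women at Week 100 while events up to Week 104 still count, which inflates the Week 104 rate

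*SAP*

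**What the plan says.** **Resumption of menses.** SAP 7.4.2.4 measures time to the "first occurrence of the menses resumption during the randomized treatment period" among women amenorrheic at Week 52/Baseline. For the others: "Patients without an event will be censored at last assessment date prior to the last dose of randomized withdrawal study drug before Week 104". Rates and their difference, with a 95% CI, are reported at Weeks 76 and 104. SAP 7.4.2.3.2 uses the same Kaplan-Meier estimates for the proportion of women whose menses has resumed.

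**Events.** SAP 4.3.1 states: "The randomized treatment period is the period when a patient was on one of the randomized study drugs". SAP 7.4.2.3.1 determines resumption by visit window. For collected products, Table 12 dates the event to the "Earliest menstruation date recorded in KCAS" data for that collection, so the event precedes the visit at which the products are returned.

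**Last dose.** A footnote to Protocol Table 1-1 states: "The last dose of study drug will be taken in the clinic during the Week 104/Early Termination visit". SAP 4.3.1 dates the last randomized dose "prior to re-treatment or on the Week 104 visit date".

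**Amenorrhea.** SAP 7.4.1.3.2 requires the definition to be met "at last two consecutive post-baseline visits prior to date of last dose of study drug during the randomized treatment period", and the same sentence carries that period through the Week 76 (or Week 104) visit. Week 76/EOT amenorrhea is the third key secondary endpoint in the fixed sequence.

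**Neighbouring rules.** SAP 7.3.1.2 censors primary-endpoint patients with complete collection and no relapse at their last available collection visit in the randomized period. Protocol 9.3.2.1 censors time-to-event endpoints at the last assessment before the end of study. For Week 104/EOT, Table 6 footnote c in SAP 4.3.7 uses the "Date of last non-missing feminine product collection within the interval from (previous visit end date + 1) to (last dose date + 7 days").

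**The concern.** A Kaplan-Meier estimate needs event-free women to stay at risk for as long as events can be recorded. Here the two limits differ: events run to the end of randomized treatment, while event-free follow-up stops before the last dose and before Week 104. For a completer that dose is taken at the Week 104 visit, so her last visit before it is Week 100. After that the risk set holds almost only women who are about to have an event, and the Week 104 rate and its treatment difference would then reflect the censoring date more than the women's bleeding.

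The amenorrhea rule raises a related question: whether an end-of-treatment endpoint includes the end-of-treatment visit.

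**Working it through.** **Inputs from the documents.** SAP Table 2 gives target days of 309 for Week 96, 337 for Week 100 and 365 for Week 104; 1 + 7 × (week − 52) reproduces all three. The protocol window at Week 100 is ±7 days, so the latest in-window Week 100 visit is Day 337 + 7 = 344. The documents give no expected number of resumptions, so every count below is assumed.

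**Estimator.** S(t) is the product of (1 − d/n) over event times up to t, where d is the number of events and n the number at risk. The resumption rate is 1 − S(365).

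**Example 1 (assumed).** Of 60 amenorrheic women in an arm, 12 resume before Week 100, one resumes on Day 350 and 47 never resume.
- Before Week 100, S = 48/60 = 0.80.
- The 47 censored at Day 337: on Day 350, n = 1 and d = 1, so S = 0.80 × (1 − 1/1) = 0. The rate is 100%.
- The 47 censored at Day 365: on Day 350, n = 48 and d = 1, so S = 0.80 × 47/48 = 0.783. The rate is 21.7%, which is 13/60.

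**Example 2 (assumed).** Of 100 women, 30 resume by Day 320, k resume on Days 350–360 and the rest stay event-free.

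| k | Event-free women censored at Week 100 (±7 days) | Censored at Day 365 |
|---|---|---|
| 0 | 30% | 30% |
| 1 | 100% | 31% |
| 3 | 100% | 33% |
| 5 | 100% | 35% |

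**Variance.** Greenwood's term is d/[n(n − d)]. With n = d its denominator is zero, so the interval for the Week 104 difference cannot be computed. The log-log interval of SAP 7.1.3 also fails, because log S does not exist at S = 0.

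**Simulation (assumed).** Constant hazard, 60 to 130 women per arm, Week 100 visits on Day 337 ± 7 and Week 104 visits on Days 365–375.

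| True Week 104 rate | Mean estimate, censoring at Week 100 | Mean estimate, censoring at the Week 104 visit |
|---|---|---|
| 10% | 35–51% | 10% |
| 20% | 55–76% | 20% |
| 30% | 67–81% | 30% |
| 50% | 83–89% | 50% |

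Under Week 100 censoring the estimate was exactly 100% in 26–58% of runs. At least one event on Days 345–365 is more frequent than that (28–93%), because a woman whose event is dated after Day 365 can hold the curve above zero at Day 365.

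**Week 76.** Completers are censored near Day 337 under the literal rule, well after Day 169, so they remain in every risk set up to Day 169. Only women stopping by about Week 76 lose a visit of follow-up.

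**Amenorrhea.** Read literally, a completer's Week 104/EOT status comes from Weeks 96 and 100 instead of Weeks 100 and 104. Under three assumed sets of visit-to-visit transition probabilities, the two rules classified 6–16% of completers differently, in nearly equal numbers each way; in one set the overall rate was 63.7% under both. For Week 76/EOT, a woman who continues past Week 76 has a later last dose, so her Week 76 visit qualifies. A woman who stops at Week 60 has only Week 56 before her last dose and cannot meet the two-visit rule.

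**The case against.** The best counter-argument is that the daily paper diary is an assessment. Three of the four resumption rules use it, and it supplies the event date when a collection is missing. A completer would then be censored at about Day 364, and Example 1 gives 21.7%, as with Day 365. This stands as a possible reading, but the SAP does not say that a diary entry sets the censoring date, and it determines resumption by visit.

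It can also be argued that 7.4.2.4 refers to the dose itself, not its date, so that products returned at Week 104 precede the in-clinic dose, and that the closing reference to Week 104 may qualify the dose. The wording allows this, but does not settle it.

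The following also stands. The endpoint is outside the testing hierarchy. Numbers at risk are to be reported, so a one-woman tail would be visible. The log-rank test is less exposed than the rate: an event whose risk set is that woman alone contributes an observed-minus-expected difference of 1 − 1 = 0.

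Three stronger readings are tempting, and the documents do not support them:
- That the Week 104 rate will be 100%. This needs a late event; with none, the curve stays at its Week 100 level, although no one is under observation at Day 365.
- That the protected amenorrhea endpoint is materially biased in a known direction. Only women stopping by about Week 76 are exposed on the natural reading. Retreated women lose no collection visit, because their last randomized dose is the day before the retreatment visit (Protocol 6.2). A bleeding final visit could be dropped in favour of amenorrhea, but a Week 60 stopper is barred from qualifying.
- That Table 6 footnote c contradicts these rules outright. Table 6 assigns diary data to windows for the product return rate, which is a different purpose. It shows that the final collection is wanted, not that two rules for one endpoint conflict.

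**Conclusion.** The concern holds for the Week 104 resumption rate, conditionally. If assessments are by-visit collections, the rule keeps events from the last four weeks and drops the event-free follow-up that belongs with them. The estimate is then biased upward. Once an event falls after the last event-free woman's Week 100 visit, the curve drops to zero at the last such event and the variance is undefined. The size depends on counts that the documents do not give; in the assumed examples one late event turns 21.7% or 31% into 100%.

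For amenorrhea the finding is unclear wording. Read literally, the sentence drops the final visit from Week 104/EOT for completers; its own closing words point the other way. The direction and size of any effect are not established, and it is probably small.

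**What to change.** In SAP 7.4.2.4, censor event-free women at their last available feminine product collection visit in the randomized treatment period, with the Week 104/Early Termination visit included, before any retreatment dose, and capped at Day 365, in line with SAP 7.3.1.2. Apply the same cut-off to events. The estimates in 7.4.2.3.2 follow automatically.

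In SAP 7.4.1.3.2, replace the restriction to visits before the date of last dose with visits on or before the date of the last randomized dose, including the Week 104/Early Termination collection.

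The cost is two wording changes and no new data. A few women's amenorrhea status may change, in either direction. The changes should be made before unblinding, so that they cannot look driven by the results.
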